# Staff Follow-up Survey (Time 2)

- 1. **Demographics:** We will re-ask questions pertaining to demographics that were skipped in the baseline survey.
- 2. Intervention acceptability, appropriateness, and feasibility: Three of the primary outcomes of this study are intervention acceptability (perceptions that the intervention is tolerable); intervention appropriateness (perceived fit and relevance of the intervention); and intervention feasibility (the extent to which the PLANTS intervention is successfully used and executed). These outcomes are measured via three scales with strong psychometric properties: structural, substantive, known-groups, and

- **4.** Active-empathic listening skills: We use the valid and reliable Active-Empathic Listening Scale containing 11 items (Bodie, 2011; Gearhart & Bodie, 2011). This scale has three domains: sensing (4 items; e.g., "I listen for more than just the spoken words"); processing (3 items; e.g., "I summarize points of agreement and disagreement when appropriate"); and responding (4 items; e.g., "I assure others that I am listening by using verbal acknowledgements"). Response options included a 7-point Likert scale ranging from "Never or almost never true" to "always or almost always true." We will calculate the mean score for the total scale. Prior research shows Cronbach's alphas range from 0.88-0.90.
- 5. Self-efficacy for working with SGMY: We assess participants' perceived abilities for working with LGBTQ high school students using 9 items adapted from the Gay Affirmative Practice Scale. Originally for social work practitioners, we adapted this scale by using school-oriented words instead of therapy-oriented words (e.g., "students" instead of "clients"). Example items included "I am able to help LGBTQ students develop positive identities as LGBTQ individuals" and "I am able to challenge misinformation about LGBTQ individuals in the classroom." Response options included a five-point Likert scale ranging from "strongly agree" to "strongly disagree." We will calculate the mean score for the scale. In a prior study, Cronbach's alpha = 0.90.
- 6. Bystander intervention behaviors for bullying: Two multidimensional scales (Teacher Bystander Intervention Model in Traditional Bullying and Cyberbullying) measuring 5 subscales of bystander behaviors: noticing the event (3 items), interpreting event as an emergency (3 items); accepting responsibility to help (3 items); knowing how to help (3 items); and implementing intervention decision (4 items). We will adapt these scales to specify SGMY-related bullying events using language from GLSEN's National School Climate Survey.
- 7. Self-efficacy of PLANTS' change objectives: Given the limited research contained validated scales of behavior change pertaining to LGBTQ inclusive practices in schools, our team has developed items pertaining directly to the self-efficacy change objectives in PLANTS. Each question will be asked on a scale of 1-5 (1: not at all certain; 2: slightly certain; 3: moderately certain; 4: very certain; 5: extremely certain).

- a. **Provide interpersonal support and affirmation.** How certain are you that you are able to successfully: ask students about their chosen names? Use students' chosen names? Ask students about their pronouns? Use students' pronouns? use "positive teacher language"? share about your personal connections to the LGBTQ+ community with your LGBTQ+ students?
- b. **Support LGBTQ+ students in meeting their basic needs.** How certain are you that you are able to successfully: offer safe locations where gender diverse youth can use the bathroom (e.g., gender neural bathrooms, staff bathrooms)? offer non-stigmatizing locations where gender diverse youth can use the bathroom (e.g., gender neural bathrooms, staff bathrooms)? Offer nearby locations where gender diverse youth can use the bathroom (e.g., gender neural bathrooms, staff bathrooms)? Offer nearby locations where gender diverse youth can use the bathroom (e.g., gender neural bathrooms, staff bathrooms)? refer LGBTQ+ students to LGBTQ affirming outside-school resources?
- c. **Provide educational resources that are inclusive of LGBTQ+ students.** How certain are you that you can successfully: find LGBTQ+ resources? put LGBTQ+ resources where students can easily access them? defend LGBTQ+ inclusive curriculum? integrate LGBTQ+ people, history, or issues into your coursework? Implement LGBTQ+ inclusivity in your curriculum? assess curriculum for LGBTQ+ inclusivity? inform students about LGBTQ+ resources?
- d. **Provide safe spaces for LGBTQ+ students.** How certain are you that you can successfully: wear iconography of LGBTQ+ pride and acceptance? display iconography of LGBTQ+ pride and acceptance for their rooms/offices? display iconography of LGBTQ+ pride and acceptance in common areas? observe LGBTQ+ related holidays and events? Establish a gender-sexuality alliance? Oversee a gender-sexuality alliance? be a Point Person? Provide LGBTQ+ students with a safe space?
- e. **Promote acceptance of LGBTQ+ students among non-LGBTQ+ students.** How certain are you that you can successfully: politely correct people who use students' incorrect names? politely correct people who use students' incorrect pronouns? teach students about LGBTQ+ terminology in a positive manner? provide positive verbal reinforcement when non-LGBTQ+ students do something LGBTQ-inclusive?
- f. **Prevent and reduce bullying, cyberbullying, and harassment of LGBTQ+ students.** How certain are you that you can successfully: define anti-LGBTQ+ bullying and harassment? implement classroom guidelines and meetings? intervene in anti-LGBTQ+ bullying and harassment? convene an anti-LGBTQ+ bullying task force when necessary? follow-up with victims and bystanders of anti-LGBTQ+ bullying? use non-confrontational ways to engage with perpetrators of anti-LGBTQ+ bullying? enforce clear consequences for people who bully others? explain to students why anti-LGBTQ+ bullying is harmful and wrong? advocate for evidence-based bullying prevention programming?
- g. Evaluate and advocate for LGBTQ+ inclusivity and protections in school policies. How certain are you that you can successfully: obtain LGBTQ+ students' feedback about the inclusivity and protections for LGBTQ+ students in existing school policies? Amend/dismantle school policies and practices that negatively affect LGBTQ+ students? evaluate how inclusive and protective their school policies are for LGBTQ+ students and staff? share statistics to advocate for LGBTQ+ inclusivity and protections in school policies? share personal stories to advocate for LGBTQ+ inclusivity and protections in school policies? use required methods (e.g., school board propositions) to create/amend school policy? examine how well your school's LGBTQ+ related policies align with local, state, and federal school laws and policies?
- h. **Maintain the confidentiality of LGBTQ+ students.** How certain are you that you can successfully: keep students' sexual orientations confidential? keep students' gender identities

confidential? make students aware of mandatory reporting guidelines? assess students' safety concerns surrounding disclosure of their LGBTQ+ identity? establish or amend school policies that protect the confidentiality of students' sexual orientations and gender identities?

8. Social desirability bias: We will re-ask questions pertaining to social desirability bias that were skipped in the baseline survey.

#### Staff Follow-up Interview (Time 3)

The purpose of this interview is to better understand trial and intervention implementation. Interview domains and questions are guided by the Consolidated Framework for Intervention Research (CFIR). Question domains include:

- Intervention characteristics: Relative advantage, adaptability, complexity, design quality and packaging
- **Outer setting:** External policies and incentives
- **Inner setting:** Structural characteristics, networks and communications, culture, implementation climate, tension for change, compatibility, relative priority, goals and feedback, learning climate, readiness for implementation, leadership engagement, available resources
- **Characteristics of individuals:** Knowledge and beliefs about the intervention, self-efficacy, individual stage of change
- Process: Opinion leaders, champions

#### PLANTS Course-embedded Questionnaires

Throughout the PLANTS program we will embed "Confidence Checks" and "Feedback" questions. Results from these items will be descriptively summarized and presented.

#### 8.2 Safety Assessments

In each staff survey, we will assess the following variables. In addition to the questions below, we will also leave open-ended text boxes so people can provide more detail on the incident.

Variables	Description	Levels/range	Justification
Parent backlash	Contact from disgruntled parents/guardians of students because LGBTQ+ inclusivity is in the classroom	Yes/no + Frequency	Parents may not be comfortable with the education their children are receiving and ask questions that educators may not be comfortable or feel safe answering.
	People attack school staff or the school for supporting LGBTQ+ youth	Yes/no + Frequency	This is happening all over the country
School board backlash	School board gets upset or concerned about staff supporting LGBTQ+ youth	Yes/no + Frequency	This is happening all over the country
Suspension or removal from employment	•	Yes/no + Frequency	This is happening all over the country

PLANTS Pilot Trial Protocol STUDY21080	178		Version 1.0 2024.04.05
Censorship of	Promotion and integration of	Yes/no +	This is happening throughout the
-	LGBTQ+ issues, history,	frequency/quantity	country
literature/history/stories	stories into the school		
or removal of books	curriculum could lead to		
with LGBTQ+	attempts to censor that		
	information by parents, school		
	boards, and higher ups in the		
	education system. Oftentimes		
	this has been justified as		
	avoiding "controversial/political		
	topics" in schools. There is the		
	possibility that teachers who		
	teach about		
	"controversial/political" topics		
	could be silenced via threats of		
	losing their jobs.		
Emotional discomfort	Staff are uncomfortable with	Likert 5-point	Some topics may provoke
with PLANTS	the training program.	scale + Open-	discomfort.
		ended	

Study team members will have contact staff and will be able to report adverse events in the appropriate case report form. In the post-trial interviews, we will interview a subset of participants who reported experiencing adverse events. We will ask questions about the AE during interviews, which will help support knowledge of the study intervention effects. We will follow-up with individuals if the event is severe (see the MOP).

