screening/enrollment and prior to intervention delivery. We will conceal allocation from schools. This is an unblinded study. This is an educational intervention that cannot be blinded because study participants will be able to tell which condition they are in based on the content they receive. Unblinding could introduce bias, including social desirability bias, attrition bias, bias in intervention participation, and bias in reporting adverse events. Outcomes are assessed via self-reported online surveys, so there is no concern about bias about the blinding for outcome assessors.

PLANTS (Providing LGBTQ+ Adolescents with Nurturance, Trustworthiness, and Safety) intervention is an online-delivered training program, including asynchronous and synchronous activities. This intervention was informed by the Information-Motivation-Behavior theory to target skills, self-efficacy, knowledge, and outcome expectations. There are approximately 20 asynchronous online modules that cover a variety of topics including lessons on LGBTQ+ terminology, names and pronouns, resources, antibullying, gender neutral bathrooms, student confidentiality, active empathic listening, and school policies. Each module includes recorded presentations, student testimonials, activities, and downloadable resources for future reference. Every month, 7-9 lessons are opened. There are 2-3 synchronous group events delivered via Zoom that are 1.5 hours each.

The active control arm is an email-based intervention, EMAILS (E-learning to Maximize Academic Inclusion of LGBTQ+ Students), in which existing public resources for supporting, affirming, and protecting LGBTQ+ are emailed to participants. All of these resources are also provided to intervention participants. The topics of the email intervention are similar to those of PLANTS.

At the 4 enrolled schools, we will administer online surveys to all staff members (i.e., a census of teachers, administrators, nurses, counselors) via REDCap software. With staff emails provided by administrators, we will send staff a screening survey, consent form, and baseline survey. Subsequently, we will sample a subset of the intervention and control groups for individual interviews to explore implementation outcomes more deeply.

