#### 5.5 Strategies for Recruitment and Retention

#### School Staff

**Recruitment.** For high schools to be eligible to enroll in our study, school administrators must be willing to provide email addresses for all school staff members so that we can adequately recruit all staff in the high school. At the enrolled high schools, we will administer online surveys via REDCap to all staff members that interact with students (e.g., a census of teachers, administrators, nurses, counselors). We will email participants a screener survey to confirm their eligibility for participation, a consent form, and a baseline survey. We will also place study advertisements in their school mailboxes.

**Retention.** The follow-up survey will be delivered post-intervention. Several methods used by [name] and his mentorship team have proven valuable in retention of participants in longitudinal studies. To keep participants engaged, we will: inform participants at the beginning about the anticipated time burden and associated incentives; provide participants with clear instructions about their tasks; send personalized reminder emails and text messages to participants who have not completed a survey; email participants 1 day in advance of their survey, reminding them to look out for the upcoming survey email and to check spam filters; encourage participants to reach out to us when they have questions or concerns via email, phone, or text; and provide participants with escalating incentives that increase each survey. We will monitor retention on a weekly basis and more frequently if needed to ensure we are maintaining high retention.

**Incentives.** To incentivize school staff to complete the baseline survey, we will provide \$20 gift cards to each participant and will raffle \$30 gift cards to 20% of participants who take the baseline survey within each school. To incentivize school staff to complete the follow-up survey, we will provide \$30 gift cards to each participant who completes the survey will and raffle \$40 gift cards to 20% of participants who take the follow-up survey within each school. For staff who complete the follow-up interview, we will provide \$50 incentive as a thank you for their time.

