#### PLANTS Course: Providing LGBTQ+ Adolescents with Nurturance, Trustworthiness, and Safety

This intervention, PLANTS Course, is an online training program for high school staff. The behavioral outcomes of PLANTS are to train high school staff to: provide interpersonal support and affirmation to SGMY; support LGBTQ+ students in meeting their basic needs; provide educational resources that are inclusive of LGBTQ+ students; provide safe spaces for LGBTQ+ students; promote acceptance of LGBTQ+ students among non-LGBTQ+ students; prevent and reduce bullying, cyberbullying, and harassment of LGBTQ+ students; evaluate and advocate for LGBTQ+ inclusivity and protections in school policies; and maintain the confidentiality of LGBTQ+ students. To achieve these outcomes, we harnessed Information-Motivation-Behavior theory to target high school staff's skills, self-efficacy, knowledge, and outcome expectations. PLANTS uses asynchronous and synchronous online activities with 3 primary sections: Trustworthiness, Safety, and Nurturance. Each section includes, as asynchronous activities, recorded presentations, student testimonials, activities, and downloadable resources for future reference. There are required synchronous Live Zoom Events delivered via Zoom that are 1.5 hours each. Live Zoom Events will be moderated by a trained interventionist and will be tailored to the need of participants. Three Live Zoom Event are offered and participants are required to complete all three. Sections are opened once a month for ~3 months. The modules were developed by my research team, including undergraduate students and graduate students with a variety of academic backgrounds, in partnership with high school staff and other professionals specialize in LGBTQ+ youth or education. We use Canvas Learning Management Software to deliver PLANTS. We will monitor intervention compliance and fidelity via module guestionnaires, Canvas informatics, event attendance, and follow-up survey questionnaires.

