# 9.4.4 Safety Analyses

Hypothesis: High school staff in the PLANTS arm will have low adverse event prevalence (≤20% of PLANTS participants will report adverse events).

We will estimate the prevalence of adverse events by calculating the percentage and 95% confidence interval of school staff that reported adverse events experienced any time after PLANTS deployment and use.

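### The parent-backlash item in section 8.2 is limited to classroom inclusivity, so it can under-count parent complaints about what PLANTS asks staff to do elsewhere in the school

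*Combined protocol and SAP*

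**What the plan says.** Section 8.2 tabulates the safety variables assessed in each staff survey. Parent backlash is described as "Contact from disgruntled parents/guardians of students because LGBTQ+ inclusivity is in the classroom", recorded as yes/no plus frequency. Its justification column speaks of parents' unease about their children's education and of questions put to educators.

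The next two rows are worded differently. One reads "People attack school staff or the school for supporting LGBTQ+ youth" (its label is lost in the text available; the section 3 table lists social media backlash in that position). The school board row reads "School board gets upset or concerned about staff supporting LGBTQ+ youth". Neither mentions a setting. Section 2.3.1 likewise names backlash for supporting SGMY as a risk without saying where the support is given.

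The intervention and the sample reach beyond the classroom. Section 4.1 lists module topics that include "gender neutral bathrooms, student confidentiality, active empathic listening, and school policies". Section 6.1.1 includes among the target behaviors that staff "evaluate and advocate for LGBTQ+ inclusivity and protections in school policies". The self-efficacy items in section 8.1 ask about bathroom access, displays in common areas, gender-sexuality alliances and amending policy. Section 5.5 recruits "all staff members that interact with students (e.g., a census of teachers, administrators, nurses, counselors").

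The benchmark in section 9.4.4 is "≤20% of PLANTS participants will report adverse events". The additional analyses in that section report event frequency by type and arm, the percentage of staff with any event (each person counted once), and the percentage of schools in each arm with any event and with each type.

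**The concern.** The item is narrower than the exposure it is meant to monitor. A parent who objects to a bathroom arrangement, a confidentiality practice, a display in a hallway or a policy change is reacting to something PLANTS encourages, yet the contact falls outside the description. Section 3 justifies the whole list of safety events as the most common and potentially the most harmful, and parent backlash is one of them. A pilot that under-records it gives the later full trial a poor basis for anticipating complaints. An event missed at the survey cannot reliably be recovered at analysis.

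**Working it through.** **1. The wording, side by side**

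| Source | Trigger | Limited to the classroom? |
|---|---|---|
| 8.2, parent backlash | Inclusivity in the classroom | Yes |
| 8.2, next row (attacks) | Supporting LGBTQ+ youth | No |
| 8.2, school board | Staff supporting LGBTQ+ youth | No |
| 2.3.1, stated risk | Supporting SGMY | No |

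Only the parent row carries the limit, and no section gives a reason for it.

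**2. Which outputs are exposed**

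- *By type.* A non-classroom parent contact is absent from the parent-backlash count. If the attack row picks it up instead, it appears under a different type, so the parent-backlash figure is still short.
- *By school.* There are four schools. If the 1:1 allocation gives two per arm, the percentage of schools with a given event type can only be 0, 50 or 100. If a school's only parent backlash is outside the classroom, the arm's figure for that type falls by 50 percentage points.
- *Overall percentage.* Each person is counted once for any event. A missed contact changes this figure only if the person has no other recorded event.

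**3. The plan's own precision figure**

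Section 9.2 gives a 95% interval width of at most 0.21 for the adverse-event proportion, with 86 PLANTS staff. The Wald width at p = 0.5 is 2 × 1.96 × √(0.25/86) = 0.211, which reproduces it. At p = 0.20 the width is 2 × 1.96 × √(0.16/86) = 0.169. Both ignore clustering by school. The benchmark of 20% corresponds to 0.20 × 86 = 17.2 staff.

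**4. Sensitivity of the overall percentage (assumed values)**

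Let *o* be the observed proportion. Let *m* be the share of staff with no recorded event who in fact had a non-classroom parent contact that every route missed. Then

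true proportion = o + m(1 − o).

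The documents give neither *o* nor *m*; the values below are assumptions chosen to show the range.

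| o | m = 0 | m = 2% | m = 5% | m = 10% |
|---|---|---|---|---|
| 10% | 10.0% | 11.8% | 14.5% | 19.0% |
| 15% | 15.0% | 16.7% | 19.3% | 23.5% |
| 18% | 18.0% | 19.6% | 22.1% | 26.2% |

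The value of *m* at which the true proportion reaches 20% is (0.20 − o)/(1 − o):

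- o = 10%: 0.10/0.90 = 11.1%
- o = 15%: 0.05/0.85 = 5.9%
- o = 18%: 0.02/0.82 = 2.4%

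At m = 0 there is no effect. The benchmark verdict changes only if the observed figure is already close to 20% or *m* is large.

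**The case against.** A reader might infer that the overall adverse-event rate is biased low. The documents do not establish that.

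- *Other routes exist.* The attack row does not exclude parents. Section 8.2 says "we will also leave open-ended text boxes so people can provide more detail on the incident" and lets study staff enter events on the case report form. Section 8.3.4 adds Live Zoom events, interviews and participant contact, gives a general question about problems at work as an example of solicitation, and requires all events on study to be documented. Any of these could record a person whom the parent item misses.
- *The net direction is open.* Emotional discomfort is scored on a 5-point scale with no stated cut-off for counting as an event. That row could push the percentage up.
- *The size depends on assumptions.* Suppose the true rate is 24%, a quarter of those reporters have only a non-classroom contact, and nothing else catches them. The measured rate is 0.24 × 0.75 = 18%. With 65 follow-up responders, the binomial chance of 13 or fewer (at or below 20%) rises from 28% to 73%. If other routes catch half of the missed cases, the measured rate is 21% and the chance is 49%. Neither the 24% nor the quarter is in the documents, and the effect looks large because the true rate was placed just above the benchmark.
- *Role.* A reader might also infer that the loss falls mostly on non-teaching staff. The documents give no mix of roles.
- *Survey text.* Section 8.2 gives descriptions and does not claim to reproduce the questionnaire verbatim, whereas section 8.1 does so for the screeners. The fielded item could be broader.

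These points defeat a claim about the overall rate, but not the narrower one. No other route is shown to be a uniform prompt for a mild parent complaint outside the classroom. The text boxes ask for detail on an incident, and a disgruntled email is not clearly an attack. The general question is only an example and is not in the section 8.2 table. Live Zoom events exist only in the PLANTS arm, and interviews reach a subsample (20 to 30 PLANTS and 10 to 20 EMAILS participants).

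**Conclusion.** The point holds as a measurement gap in one item. Read as written, the parent-backlash variable is narrower than its neighbours, than the stated risk, and than the settings and roles PLANTS targets. It can under-count parent backlash by type and by school.

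An effect on the overall percentage is possible but unquantified. It requires staff whose only event is a non-classroom parent contact that every other route misses, and it would alter the benchmark conclusion only in the circumstances shown in step 4 of the working. The conclusion assumes that the survey follows the section 8.2 description and that respondents take the classroom limit literally.

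**What to change.** Reword the item as: *contact from disgruntled parents/guardians because of support for, or inclusion of, LGBTQ+ students anywhere at the school*. Use identical wording in both arms and in both the baseline and follow-up surveys, so that the arms and time points are comparable and the scope matches the adjacent rows. If the questionnaire is already this broad, correct the section 8.2 description to match it.

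The cost is one line in the protocol and the survey. The downside is that the reported adverse-event percentage may be slightly higher.

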#### Additional Analyses

We will report overall frequency (adding together all the adverse events reported) of adverse events by study arm, followed by the frequency of all types of adverse events by study arm. We will also report the total number of adverse events by severity and average duration, overall and by arm. We will also examine the frequency and percentage of school staff reporting adverse events (which will be counted once only for a given participant). We will also calculate adverse events by school level. We will report study arm-specific percentages of schools that had staff who reported any adverse event and by each type of adverse event.

Study arms will be compared on baseline characteristics (e.g., demographics) using descriptive statistics. We will test for differences in potential confounders between intervention and control arms using baseline staffand school-level data with Rao-Scott chi-square tests for categorical variables and linear mixed models (with a random effect for school) for continuous variables (models adjusting for the clustering of staff within schools).

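### Adverse event totals add up staff reports, so one school-wide incident can be counted once for each colleague who reports it; the totals need a distinct-incident rule

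*Combined protocol and SAP*

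**What the plan says.** Section 8.2 puts the safety items in each staff survey. Most are answered yes or no with a frequency, and open text boxes allow more detail. Several items are not confined to what happened to the respondent. The school board item reads "School board gets upset or concerned about staff supporting LGBTQ+ youth". The attack item allows the school itself to be the target. The censorship item, as listed in Section 3, includes books taken out of school libraries. For several of these items the stated justification is "This is happening all over the country".

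Section 9.4.4 uses these reports in three ways:

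- **Benchmark.** The hypothesis is "≤20% of PLANTS participants will report adverse events", to be assessed by "calculating the percentage and 95% confidence interval of school staff that reported adverse events experienced any time after PLANTS deployment and use".
- **Event totals.** Under Additional Analyses: "We will report overall frequency (adding together all the adverse events reported) of adverse events by study arm". Totals by type, by severity and by average duration follow.
- **Staff and school summaries.** The number and percentage of staff reporting any event is given separately, "which will be counted once only for a given participant". At school level, "We will report study arm-specific percentages of schools that had staff who reported any adverse event and by each type of adverse event".

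The once-only rule works within a participant. The protocol gives no rule for combining reports of the same incident from several participants at one school.

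**The concern.** A total described as a number of adverse events should count events. Where an event belongs to a school and every enrolled colleague is asked about it, a sum of reports counts how many colleagues noticed it. The number then depends on how visible the incident was and how many staff enrolled at that school. Average duration is affected too, because a widely noticed incident is weighted by its number of reporters. Comparing arms does not remove the problem, since the same items are asked in the EMAILS schools and the inflation there depends on the same accidents of visibility and enrolment.

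The 20% benchmark raises a related but different question. With only two PLANTS schools, one shared incident can supply enough reporters to exceed the limit with no report from the other school. A reader of the percentage alone could not tell that from many separate personal events. The pilot is meant to inform a fully powered trial, so both figures are likely to be carried forward.

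**Working it through.** **Inputs.** There are four schools allocated 1:1, so two are PLANTS schools (Section 6.3). Section 9.2 gives 344 staff invited, 50% participation, half of participants in PLANTS, and 75% of PLANTS participants completing follow-up. An equal split between the two PLANTS schools is an assumption.

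**The plan's own figures.** 344 × 0.5 × 0.5 = 86 PLANTS staff, and 86 × 0.75 = 64.5, stated as 65. Section 9.2 gives a maximum 95% CI width of 0.21 for the adverse event proportion. The simple binomial formula gives 2 × 1.96 × √(0.25/86) = 0.211, so the figure reproduces. That formula treats staff as independent.

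**Event total from one incident.** Equal schools give 86/2 = 43 enrolled staff per school and about 32 follow-up completers.

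- Every completer at one school reports: about 32 entries for one event.
- Every enrolled participant there reports: 43 entries for one event.
- Any respondent who enters a frequency above 1 could raise the total further.

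**Reporters needed to exceed 20%.** The smallest number is floor(0.20 × n) + 1.

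- n = 86: 0.20 × 86 = 17.2, so 18 are needed; 18/86 = 20.9%, and 18/43 = 42% of one school.
- n = 65: 0.20 × 65 = 13, so 14 are needed; 14/65 = 21.5%, and 14/32 = 44% of one school's completers.
- Only completers can report but the denominator stays at 86: 18/32 = 56% of one school's completers.

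**Sensitivity to the assumptions (n = 86).**

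- School split: if the affected school holds 30% of the arm (26 staff), the share needed is 18/26 = 69%. If it holds 70% (60 staff), it is 18/60 = 30%.
- Background: suppose unrelated events affect a fraction b of all staff. The share needed is q = [(18 − 43b)/43 − b]/(1 − b), which is 34% at b = 0.05 and 24% at b = 0.10.
- Chance of exceeding 20% with no background, if each of 43 participants reports the incident with probability q (simulation, 200,000 draws): 7% at q = 0.3, 46% at 0.4, 89% at 0.5 and 99% at 0.6.
- For contrast, independent personal events at 10% and no shared incident exceed the limit with probability 0.002.

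**Effect on precision.** Shared incidents make reports within a school alike. With an assumed ICC of 0.01, 0.05 or 0.10, the design effect 1 + 42 × ICC is 1.42, 3.1 or 5.2. The width of 0.211 becomes about 0.25, 0.37 or 0.48.

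**The case against.** The strongest reply is that the person-level percentage is not double counting. If board hostility reaches 20 staff, then 20 staff were exposed, and Section 8.3.3.1 grades severity by the effect on the participant at work. That stands. A reader might infer that the 20% benchmark is wrongly constructed, or should be limited to events aimed at the respondent. The documents do not support this. Section 3 lists backlash and censorship among the events that could most harm staff, and removing shared events would make the limit easier to pass.

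A reader might also infer that the safety verdict depends on a background incident and not on PLANTS. That goes too far. Exceeding 20% requires a large share of one school to report the incident, and the documents give no such share. Section 8.3.4 excludes events already present at screening, which removes some background. No stopping or progression rule uses the 20%: interim analyses are not planned (Section 9.4.6), and the listed grounds for suspension do not cite it.

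Much of the needed context is already planned: summaries by arm, type and school, and a case report form with description and onset (Section 8.3.4). A cluster at one school would probably be seen. None of these provisions says how duplicate reports enter the total, so that gap remains.

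Some items can also be personal. The attack item covers individual staff, and the censorship item mentions threats to jobs. The item table is partly broken in the available text, and the manual of procedures, which is not in the documents, might hold a rule. Finally, 43 entries is an upper figure: if reports come only through the follow-up survey, 75% completion limits it to about 32. Section 8.3.4 does allow other routes, including Live Zoom events, interviews and direct contact.

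**Conclusion.** The point holds for the event totals. As written, they sum reports, and one school-wide incident can be counted about 32 times, or up to 43, where one event occurred. This rests on the plan's recruitment and completion figures, an equal split between the two PLANTS schools, and every completer or every participant at the affected school reporting. With fewer reporters the inflation shrinks in proportion.

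For the 20% benchmark the conclusion is narrower. It is a legitimate measure of staff affected, but one shared incident can breach it if at least 18 of 86 staff, or 14 of 65 completers, report it. The share of one school this represents runs from 30% to 69% across the splits examined at n = 86. The issue is therefore one of interpretation: the plan should let a reader see whether a breach came from one incident or many. The primary endpoints are unaffected.

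**What to change.** Add a short paragraph to Section 9.4.4:

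- Name the event types treated as school-wide: school board backlash, attacks on the school, and censorship or book removal.
- Define a distinct incident by school, event type, onset and description, using the survey free text and the case report form.
- For these types, report distinct incidents per school and arm alongside the number of staff reporting, and use distinct incidents in the event totals and the duration summary.
- Keep the 20% person-level benchmark. Next to it, show the EMAILS percentage and a breakdown by school and by personal versus school-wide event type.
- If a confidence interval for the arm difference is given, it must allow for clustering and be described as very imprecise, with two schools per arm.

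The data needed are already planned: the survey collects free text, and onset is recorded on the case report form. The cost is a small adjudication step to match reports, with some judgement where dates or descriptions are vague.
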